11.6.1 Primary Estimand

The primary estimand corresponding to the primary endpoint is defined as:

Treatment: Participants will be randomised to receive plitidepsin versus control in each group.

Population: Participants as defined through the inclusion and exclusion criteria, who have been randomised to the trial and who have taken at least 1 dose of study treatment (plitidepsin or control).

Variable:

–1-month all-cause mortality rate (Day 30 since randomisation).

Intercurrent events:

- The participant's data are collected and included in the analysis without regard for treatment discontinuation (treatment-policy strategy).
- In the event of the participant initiating another non-protocol therapy, 1-month all-cause mortality rate will be evaluated regardless of initiation of new non-protocol therapy (treatment-policy strategy).

Population level summary: the posterior probability associated for the odds ratio of 1-month all-cause mortality rate from a Bayesian logistic regression for each group comparison including point estimate and credible interval will be shown.

The cut-off for considering further clinical development of plitidepsin in each randomized group will be a posterior probability of superiority for the experimental arm equal to or greater than 65%.

<NOTE: Due to the premature study closure no Bayesian specific outputs will be generated and descriptive data will be shown>.

11.6.2 Key Secondary Estimand

The key secondary estimand corresponding to the key secondary endpoint is defined as:

Treatment: Participants will be randomised to receive plitidepsin versus control in each group.

Population: Participants as defined through the inclusion and exclusion criteria, who have been randomised to the trial and who have taken at least 1 dose of study treatment (plitidepsin or control).

Variable:

–Time to confirmed negativisation in SARS-CoV-2 antigen test or RT-PCR Ct > 30 calculated as date/time of survival event – first dose date/time of Investigational Product administration.

Intercurrent events:

- The participant's data are collected and included in the analysis without regard for treatment discontinuation (treatment-policy strategy).
- In the event of the participant initiating another non-protocol therapy, time to confirmed negativisation will be evaluated regardless of initiation of new non-protocol therapy (treatment-policy strategy).

Population level summary: the hazard ratio from a Cox regression for each group comparison including point estimate and confidence interval will be shown.

<NOTE: Due to the premature study closure no complex specific outputs will be generated and descriptive data will be shown>.

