- Review of safety/efficacy trends, such as an accumulating number of deaths in the study (i.e., from administration of the first dose of study drug on Day 1 through Day 60), to determine if there is a difference between plitidepsin and control groups and potential impact on study conduct.
- Each group will proceed with per protocol pre-established recruitment and follow-up and the IDMC Support Team will provide the IDMC Chairperson with unblinded information on the number of deaths and SAEs. Upon review of this data, if either the difference in the percentage of patients with deaths or SAEs Grade ≥ 3 is at least 20% higher in any IMP group in comparison with the Control Group, IDMC Chairperson will contact the other members of the IDMC to assess the continuity of the other groups.

The IDMC can ask for a temporary halt of the clinical trial at any time to better analyse any potential benefit/risk concern.

Study “Stopping rules”

The Sponsor may suspend or terminate the study if:

- New toxicological or pharmacological findings or safety issues that invalidate the earlier positive benefit-risk assessment occur;
- Significant safety concerns, according to the Sponsor’s criteria, arise during the conduct of the study;
- The development of plitidepsin is discontinued;
- Any other reason (e.g., best interest of the patients, accrual rate makes the completion of the study feasible, etc.) leads to this suspension or termination.

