8.2 Overall Design

This is a multi-centre, randomised, controlled, open-label, pragmatic, phase 2 basket study to assess the efficacy and safety of plitidepsin in different groups of immunocompromised patients with coronavirus disease 2019 (COVID-19) who require hospital care.

More than 50 sites are planned to participate in this study worldwide.

[figure not shown]
Approximately 150 patients are foreseen for the study, divided in 4 different groups of immunocompromised patients:

- Group 1 –Patients receiving immune-suppression due to haematopoietic or organ transplantation.

- Group 2 – Patients receiving B-cell depleting therapies.
- Group 3 – Patients receiving other immune-suppressive therapies.
- Group 4 – Other situations with immune deficiencies.

Whenever a patient can be allocated to more than 1 group, the priority will be group 1 > group 2 > group 3 > group 4. In groups 1, 2, and 3, patients will be randomised to receive best standard care (BSC) ± other antiviral (if clinically indicated) on control arm and BSC + plitidepsin on experimental arm. Group 4 will not be controlled (it was not applicable in Spain), as shown in Figure 8.2.1.

Figure 8.2.1. Algorithm for Patient Assignment in NEREIDA Basket Trial.

Stratification:

- Group 1: ISARIC mortality (<9/≥9) | Type of graft (allogeneic haematopoietic/lung or intestinal/other)
- Group 2: ISARIC mortality (<9/≥9) | Disease (haematological neoplasm/other)
- Group 3: ISARIC mortality (<9/≥9) | Disease (neoplasia/other)
- Group 4: Not applicable

Study periods:

The study will include a Screening period, a Treatment period and a Follow-up period.

Refer to the Schedule of Assessments (Protocol Appendix 13) for data to be collected.

The Screening period starts once the patient has provided written informed consent and ends when the patient is randomized (allocated in group 4) in the study. Parameters assessed during this time will serve as the baseline values. The screening procedures should be preferably performed within 24 h prior to administration of study treatment, allowing a maximum of 48 h prior to administration of study treatment if required.

The Treatment period starts on Day 1 (date of randomisation) to 24 h after the last dose of the antiviral therapy; if no antiviral was given in the control arm, then the treatment period will finish on Day 4, for data management purposes. Antiviral treatment must always be started on the randomisation date.

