The Follow-up period starts after the end-of-treatment and lasts until the end-of-study.

The End of Study (EOS) is Day 60 (± 3) or date of early study termination unless ongoing SAEs, if applicable.

The End of Trial (EOT) will be when the Last Patient Last Visit (LPLV) has occurred.

All patients will receive the best available care as per applicable local, institutional, national, supranational COVID-19 treatment guidelines.

Patients assigned to the experimental arms will receive, in addition, plitidepsin as a 1-h IV infusion, during Days 1 to 3.

Patients randomised to the control arm may receive a regulatory-approved antiviral treatment in addition to the BSC.

For prevention of infusion-related (i.e., plitidepsin-related) reactions (IRRs), allergic reactions and emesis reactions, administration of premedications is mandatory in the experimental arms.

All consenting patients discontinuing early from the study before the EOS visit should complete the early termination/withdrawal procedures.

Duration of Study Periods:

- Screening period: From the day of ICF signing prior to randomisation).
- Day 1: Date of randomisation. Treatment must be started on the same date.
- Treatment period: from Day 1 to 24 h after the last dose of the antiviral therapy; if no antiviral was given in the control arm, then the treatment period will finish on Day 4, for data management purposes.
- Follow-up period: From the end-of-treatment to end-of-study.
- EOS: Day 60 (± 3) or date of early study termination unless ongoing SAEs, if applicable.
- Overall study duration: 60 (± 3) days since randomisation.
- End of the trial will be when the Last Patient Last Visit (LPLV) has occurred.

Independent Data Monitoring Committee (IDMC):

An IDMC was established to provide study oversight. The IDMC was composed of individuals external not only to the Sponsor but also to the trial managers (including Sponsor's and Contract Research Organisation's [CRO] medical monitors) and study investigators.

Given the decision to terminate the study due to low accrual, the IDMC activity has been discontinued and there will not be distinction between blinded and unblinded procedures.

Study “Stopping rules”

The Sponsor may suspend or terminate the study if:

- New toxicological or pharmacological findings or safety issues that invalidate the earlier positive benefit-risk assessment occur;
- Significant safety concerns, according to the Sponsor’s criteria, arise during the conduct of the study;

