8.4 Randomisation

Patients will be sequentially allocated in their respective group, following the algorithm depicted in Figure 8.2.1.

Central randomisation will be implemented by means of RTSM Rave, for full details on how the randomization lists are created and block selection see the randomization plan. In groups 1-3, patients will be assigned to the experimental or the control arms at a 1:1 ratio. Stratification will be performed in the randomised groups. The ISARIC-4C mortality score will be used as a stratification factor in all groups (score <9/ \geq 9). In addition, the type of graft (allogeneic haematopoietic/lung or intestinal/other) will be used for Group 1, whereas the underlying disease will be considered for Groups 2 and 3. For Group 2, the factor categories will be haematological neoplasm vs other disease; the respective categories for Group 3 will be neoplasia vs other. Stratification is not applicable in the non-randomised Group 4.

Day 1 is defined as the day of randomisation. Treatment must start within the same natural day.

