8.6.2.1 Full Analysis Set (FAS) Population

All randomised patients who have taken at least 1 dose of study treatment (plitidepsin or control) and have completed follow-up for survival until day 30 (± 2). Patients who die before the end of follow-up period will also be included in the FAS population. FAS population will be analysed according to their randomised treatment arm.

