As each basket completes, they would have been evaluated for efficacy, with information gained being used to update the analyses of successive baskets.

Due to the premature study closure no Bayesian specific outputs or sensitivity analyses will be generated

Secondary Endpoints/Other Endpoints

Frequency tables will be prepared for categorical variables, and continuous variables will be described by means of summary tables, which will include the median, mean, standard deviation, interquartile range, minimum, and maximum of each variable.

Frequentist methods will be calculated. Counts and percentages, with their corresponding exact confidence intervals, will be calculated for the binomial endpoints.

Time-to-event variables (e.g. key secondary endpoint) and their set time estimates will be defined as time from randomization to their corresponding event + 1 (see 8.3 section) and analysed according to the Kaplan-Meier method.

Key secondary endpoint, time to confirmed negativisation in SARS-CoV-2 antigen test or RT-PCR Ct > 30, will be analysed according to the Kaplan-Meier method.

<NOTE: Due to the premature study closure no complex specific outputs or sensitivity analyses will be generated>.

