11.8 Summary of Statistical Tests

All the main characteristics for estimands to fulfill study objectives will be defined as footnotes in each table following a similar structure than primary estimand definition. Below it can be found the endpoints to measure the variable definition and the analysis method to be used. Treatment attribute is maintained as 'participants will be randomised to receive plitidepsin versus control in each group' whereas applicable and sensitivity analyses according populations defined in 8.5 will be calculated. For intercurrent events, while applicable, a treatment-policy strategy as defined for the primary estimand will be followed.

Table 3 Summary of statistical tests

Endpoints	Analyses	Population
Efficacy primary endpoint		
1-month all-cause mortality rate.	-Frequencies	-FAS population
Key secondary endpoint		
Time to confirmed negativisation in SARS-CoV-2 antigen test or RT-PCR Ct > 30.	-Kaplan-Meier (unstratified)	-FAS population

Endpoints	Analyses	Population
Efficacy secondary endpoints		
Time to sustained end of COVID-related hospital care from the time of randomisation. Sustained discharge is defined as no subsequent admission within 30 days of initial end of hospital care [up to day 60 (± 3)], related to either COVID-19 or COVID-19 therapy	-Kaplan-Meier (unstratified)	-FAS population
Time to sustained improvement (defined in Protocol Section 7.1.3) and resolution of selected COVID signs/symptoms (See Protocol Appendix 10 - COVID-19 signs/symptoms checklist).	-Kaplan-Meier (unstratified)	-FAS population
Distribution of patients according to their clinical status by the 11-category WHO Clinical Progression Scale, at Days 4 (± 1), 8 (± 1), 15 (± 1), 30 (± 2), and 60 (± 3) (See Protocol Appendix 1 – 11-Point World Health Organization (WHO) Clinical Progression Scale).	-Frequencies	-FAS population
Percentage of patients requiring oxygen therapy on Days 4 (± 1), 8 (± 1), 15 (± 1), 30 (± 2), and 60 (± 3).	-Frequencies	-FAS population
Time to sustained discontinuation (i.e., at least 7 days) of oxygen supplementation.	-Kaplan-Meier (unstratified)	-FAS population
Safety secondary endpoints		
Treatment-emergent adverse events (TEAEs).	-Frequencies (severity grade by NCI-CTCAE v5)	-As treated population
TEAEs \geq grade 3 according to the National Cancer Institute	-Frequencies	-As treated population

Endpoints	Analyses	Population
[NCI]-Common Terminology Criteria for AEs (CTCAE v.5.0).		

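### The key secondary endpoint has two time formulas in current SAP text, and the one in 11.6.2 gives no start time to a control without an Investigational Product dose

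*SAP*

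**What the plan says.** Two parts of the SAP define the time variable for the same endpoint.

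- SAP 11.6, in its text on secondary endpoints, gives a rule for time-to-event variables and names the key secondary endpoint as an example. These variables "will be defined as time from randomization to their corresponding event + 1".
- SAP 11.6.2, the key secondary estimand, subtracts the "first dose date/time of Investigational Product administration" from the date and time of the event. It adds no day.

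SAP 8.3, to which 11.6 refers, lists the endpoint without a starting point, as does protocol 3.2. The endpoint is still reported: SAP 11.8, Table 3, plans "Kaplan-Meier (unstratified") in the full analysis set (FAS).

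On dosing, SAP 8.4 defines Day 1 as the day of randomisation and adds: "Treatment must start within the same natural day". In the control arm an antiviral is optional. SAP 8.2 says "Patients randomised to the control arm may receive a regulatory-approved antiviral treatment in addition to the BSC", and it provides for controls who get none: "if no antiviral was given in the control arm, then the treatment period will finish on Day 4". The FAS in SAP 8.6.2.1 is "All randomised patients who have taken at least 1 dose of study treatment (plitidepsin or control"), with survival follow-up to Day 30 or death before the end of follow-up.

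**The concern.** Two programmers, each following the SAP faithfully, could print different times for the same patient. SAP 11.8 also says that estimand characteristics will appear as table footnotes, so a table could carry the 11.6.2 definition beneath times computed by the 11.6 rule.

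The second issue is one-sided. Every patient who receives plitidepsin has a first Investigational Product dose, but a control need not. A programmer using 11.6.2 would have to leave out such a control or invent a start time, and this could happen only in the control arm. What is at stake is the accuracy and labelling of the Kaplan-Meier curves and medians for the key secondary endpoint. No test result is at stake.

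**Working it through.** The documents give no figure for this endpoint that could be reproduced, so the check applies both written rules to the same dates.

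**1. Size of the offset in dosed patients.** Let d be the study day of the event (randomisation = Day 1). Let a and b be the clock times of the first dose and of the event sample, as fractions of a day. The dose falls on Day 1 (SAP 8.4).

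- SAP 11.6: (d − 1) + 1 = d.
- SAP 11.6.2: (d − 1) + b − a.
- Gap: 1 + a − b. As a and b each lie between 0 and just under 1, the gap is more than 0 and less than 2 days. It is exactly 1 when a = b.

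| Event day | SAP 11.6 | SAP 11.6.2, a = b |
|---|---|---|
| 4 | 4 | 3 |
| 8 | 8 | 7 |
| 15 | 15 | 14 |

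Example with clock times: dose at 14:00 on Day 1, event sample at 10:00 on Day 4. SAP 11.6 gives 4. SAP 11.6.2 gives 3 + 10/24 − 14/24 = 2.83. The gap is 1.17 days.

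When one rule is used for everyone, the offset is much the same in both arms and shifts the curves together.

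**2. Which controls have no start time under SAP 11.6.2.** This depends on two terms that the documents leave open.

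| Investigational Product means | Best standard care alone is a control dose | FAS controls without a start time |
|---|---|---|
| plitidepsin only | yes | all |
| plitidepsin only | no | all (each had an antiviral; the others are outside the FAS) |
| also a control's approved antiviral | yes | those given no antiviral |
| also a control's approved antiviral | no | none |

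SAP 9.0 does not fill the gap. It censors patients with no data for an endpoint at time 0, but these controls have data and lack only an origin. Under SAP 11.6 every randomised patient has an origin, so the question does not arise.

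**3. A side question: a Day 1 sample taken before dosing.** Protocol 4.1 allows entry on a positive antigen test alone. Protocol 7.1.1 takes the central PCR on Day 1 before treatment, and it writes a confirmation step for the antigen test only. If a Day 1 Ct above 30 were counted as the event, its time would be 1 under SAP 11.6 and b − a, below zero, under SAP 11.6.2. For a patient whose Ct stays above 30, a post-baseline rule would move a PCR-based event to the Day 4 (±1) sample, time 3 to 5 under SAP 11.6. That is a shift of 2 to 4 days.

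**The case against.** The case for leaving the text alone has substance.

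- The mismatch is small. With same-day dosing it is about one day, SAP 6.0 rules out formal significance tests, and the note closing 11.6.2 drops complex outputs in favour of descriptive data. SAP 11.6 is the methods text for the surviving Kaplan-Meier analysis and is the natural rule to follow. All of this stands, and it limits the weight of the point. But the note does not withdraw the first-dose formula, and nothing says which rule prevails.
- The missing origin is conditional. If Investigational Product means study treatment in general, and best standard care alone is not a dose, no analysed control lacks an origin. This also stands: the last row of the second table is a possible reading, though not the only one.

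A reader might go further and infer that the whole control arm, 3 × 20 = 60 of the 120 planned randomised patients, has no start time. The support would be the protocol's safety-monitoring trigger in section 3, where a difference "is at least 20% higher in any IMP group in comparison with the Control Group" prompts a review. That sentence sets the two apart, but it does not define the term used in the SAP. The 60 is also a planned figure: the SAP reports early closure for low recruitment, and the documents reviewed give no actual counts.

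A reader might also infer a false advantage for plitidepsin, with its arm timed by 11.6.2 and controls by 11.6. That would be an offset of about one day, but no section prescribes such a mixture.

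Finally, a reader might infer that baseline PCR results will be counted as clearance. Protocol 7.1.1 uses Day 1 as the reference for viral-load change, and SAP 9.0 defines baseline as the latest test up to drug administration. Protocol 5.5.1 requires eligibility still to hold on the assessments closest to first dosing, which narrows the scenario without closing it. Appendix 13, to which SAP 9.0 refers for trial days, was not among the documents reviewed, and no frequency is known. This is missing detail, not a demonstrated error.

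**Conclusion.** The SAP is wrong as written on one definite matter: it holds two incompatible time formulas for one endpoint that it still reports. In dosed patients the difference is about one day (strictly between 0 and 2 by clock time), with little effect on the comparison between arms. This rests on treatment starting on the randomisation day, as SAP 8.4 requires.

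The 11.6.2 formula is also unusable for any FAS control without an Investigational Product dose. The number of such controls runs from none to all of them, depending on two undefined terms, and the documents do not allow a narrower statement. Any gap falls on the control arm alone.

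The consequence is confined to descriptive curves, medians and footnotes. The correction is worth making because it costs almost nothing and concerns the key secondary endpoint; the trial's conclusions do not turn on it. The Day 1 sample question does not carry the point and merits a clarifying line at most.

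**What to change.** Delete the first-dose formula from SAP 11.6.2 and state that the endpoint is timed from randomisation (Day 1, with the added day) in both arms, as SAP 11.6 already says. Use the same definition in the table footnotes foreseen in SAP 11.8. Because SAP 8.2 records a decision on 19 March 2024 to unmask the data, document the change as made after that decision.

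Optionally, add one sentence saying that only post-baseline results count as events, and another saying whether confirmation is required for an RT-PCR Ct above 30.

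The cost is a few lines of SAP wording. No new data, curves or sensitivity analyses are needed, since a randomisation date exists for every randomised patient.

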11.7 Safety Analyses

Safety analyses will be based on the As Treated Population. All safety parameters will be summarised, plotted and also listed by patient/events.

A treatment-emergent adverse event is defined as any event not present prior to the initiation of the treatments or any event already present that worsens in intensity following exposure to the treatments.

Treatment-emergent Adverse Events: The verbatim terms used in the electronic case report form (eCRF) by investigators to identify TEAEs will be coded using the Medical Dictionary for Regulatory Activities (MedDRA) and will be graded according to NCI CTCAE version 5.0. Treatment-emergent AEs will be summarised by MedDRA system organ class and preferred term by number of patients and by number of events. For each TEAE, the percentage of subjects who experience at least 1 occurrence of the TEAE will be summarised overall and by treatment group. The SAEs, AEs of special interest, and deaths will be listed including the study period (see Section 8.2) that they occur. All TEAEs resulting in discontinuation of study treatment will be listed and summarised by system organ class/preferred term.

AEs, SAEs, deaths, laboratory evaluations, and study drug discontinuations due to AEs will be tabulated in a descriptive way. Counts and percentages will be used for categorical variables, and summary tables will be used for continuous variables.

Any treatment-related adverse events (including Unknown relationship but potentially related), treatment-emergent adverse events of special interest, and SAES (including those with seriousness missing) that will be measured daily until resolution or stabilisation to at least Grade 1, or to an acceptable level according to the investigator and the sponsor of his/her designated representative.

Clinical Laboratory Tests, see protocol sections 5.5.1/5.7/5.8/5.9 and appendix 8 to differentiate local or central. Laboratory data will be summarised by type of laboratory test. The worst toxicity grade will be tabulated. Parameters with predefined NCI CTCAE version 5.0 toxicity grades will be summarised. Change from baseline to the worst TEAE grade experienced by the subject during the study will be provided as shift tables.

- Haematology: haematocrit, red blood cells (RBC), differential WBC counts (including neutrophil and lymphocyte counts), platelet count and haemoglobin.
- Biochemistry: Liver function test [ALT, AP, AST, albumin, total bilirubin (direct bilirubin if total is abnormally elevated)], lactate dehydrogenase (LDH), glucose [fasting], sodium, potassium, calcium, BUN/urea, gamma glutamyl transferase (GGT), creatinine, calculated creatine clearance [Chronic Kidney Disease Epidemiology Collaboration (CKD-EPI)], CPK, amylase, lipase, pro-calcitonin, ferritin, and CRP.
- Coagulation (D-Dimer).
- Urine analysis (semi-quantitative elemental tests for specific gravity, blood, pH, proteins, bilirubin, glucose, ketones, nitrites, and qualitative analysis of the sediment).

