1.2.1.3.2 Effects of Plitidepsin in Immune System

An integrated analysis on the safety of the recommended doses for Phase 2-3 clinical trials have been done on a total of 419 cancer patients after their first infusion of treatment (cycle 1/Day 1) (Please refer to the IB of plitidepsin). This analysis also evaluated the potential immunosuppressive effects of plitidepsin based on the following parameters:

- Incidence of infections: The most significant side effect of immunosuppressive drugs is an increased risk of infection. Among the 419 cancer patients, 47 (11.21%) patients experienced 55 infections after their first infusion of treatment (cycle 1/Day 1), none of which were considered by Investigators to be related to study drug. A total of 21 infections in 19 (4.5%) patients were reported as SAEs, resulting in prolonged hospitalisation for 18 patients and death of one patient as a result of a pneumococcal infection and sepsis. Among SAEs for infection, those reported in more than one patient were pneumonia (7 patients), respiratory tract infection (3), sepsis (2) and infection (2).
- Incidence of lymphopenia and neutropenia: Lymphopenia and neutropenia increase susceptibility to infection. Among the 419 cancer patients, there were no reports of lymphopenia and reports of neutropenia (grade 3) for only 3 (0.7%) patients after the first infusion of treatment (cycle 1/Day 1). The low incidence of neutropenia and absence of lymphopenia support Investigator assessments that AEs of infections were unrelated to plitidepsin treatment.
- Incidence of laboratory abnormalities in lymphocytes and neutrophils: Shift tables for the change from baseline to the worst grade on study for lymphocyte count and neutrophil count showed new or worsening decreases in lymphocyte count for 15.5% (61/394) of evaluable patients and new or worsening decreases in neutrophil count for 9.9% (24/396) of evaluable patients. Most patients (75.9% [299/394]) had grade 0-1 lymphocyte count at baseline and only 4 (1.3%) of these patients developed grade 3 lymphocyte count decrease on study.

Similarly, most patients (85.9% [340/396]) had grade 0-1 neutrophil count at baseline and only 1 (0.3%) developed grade 3 neutrophil count decrease on study. The variation of lymphocytes counts and neutrophil counts after the first infusion of treatment (cycle 1/Day 1) is presented in [Figure 4](#) and [Figure 5](#), respectively.

[figure not shown]

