Laboratory Abnormalities: Laboratory abnormalities will be recorded and graded according to NCI-CTCAE version 5.0, accessible via internet (http://ctep.cancer.gov/protocolDevelopment/electronic_applications/docs/CTCAE_v5_Quick_Reference_8.5x11.pdf). Laboratory abnormalities that are of clinical significance will be recorded in Adverse Event eCRF.

Laboratory abnormalities for which NCI CTCAE grading is not available will be classified as the fold below the lower limit of normal (<LLN) or fold above the ULN.

All AEs will be graded according to the NCI-CTCAE v.5. Treatment modifications and reason for treatment discontinuation will be monitored throughout the study. The latest MedDRA dictionary version will be used for AE coding.

The safety profile of patients will be monitored throughout the treatment and at Day 60 (± 3 days), or until the date of death, whichever occurs first.

Any treatment-related AEs, treatment-emergent adverse events of special interest, and SAEs will be measured daily until resolution or stabilisation to at least Grade 1, or to an acceptable level according to the investigator and the Sponsor of his/her designated representative.

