7.4 ADVERSE EVENTS REPORTING PROCEDURES

7.4.1 Reporting of Adverse Events

The Sponsor will collect AEs from ICF signature until Day 60 (± 3 days) or until the date of death, whichever occurs first. All AEs suspected to be related to the study drug/IMP must be followed-up after the time of therapy discontinuation until the event or its sequelae resolve or stabilize at an acceptable level to the Investigator and the Sponsor.

All AEs, including medication errors and uses outside what is foreseen in the protocol, must be recorded in English using medical terminology in the source document and the e-CRF. Whenever possible, the Investigator will record the main diagnosis instead of the signs and symptoms normally included in the diagnoses.

Investigators must assess severity (grade) of the event following the NCI-CTCAE v.5 and assign a relationship to each study drug(s)/IMP(s); and pursue and obtain information adequate both to determine the outcome and to assess whether it meets the criteria for classification as a SAE requiring immediate notification to the Sponsor or its designated representative. The Investigator must provide any relevant information as requested by the Sponsor in addition to that already provided in the e-CRF.

Abnormal laboratory tests occurring during the study should only be recorded in the AE section of the e-CRF if the disorder:

- Is associated with clinically significant symptoms, and/or
- Leads to a discontinuation from the study, significant additional concomitant drug treatment or other therapy, and/or
- Leads to any of the outcomes included in the definition of a SAE.
- The test result is considered to be clinically relevant by the Investigator.

Otherwise laboratory results should be reported in the corresponding section of the e-CRF (e.g. biochemistry, haematology).

Signs and symptoms: all signs and symptoms present since the diagnosis of SARS-CoV-2 infection will be collected, including those related with the underlying disease or other concomitant conditions only if present at the time of ICF signature. A separate focus will be done on targeted COVID-19 signs and symptoms present within the last 24 h prior to screening and listed in [Appendix 10](#). They will be also monitored separately by the research team and collected in a specific form of the CRF.

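### Laboratory shift tables run from baseline to worst TEAE grade, which names the wrong data source; the end point should be the worst post-baseline laboratory grade

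*SAP*

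**What the plan says.** In SAP 11.7, the paragraph on clinical laboratory tests first promises a worst-grade table ("The worst toxicity grade will be tabulated") and a summary of parameters that have CTCAE v5.0 grades. It then defines the shift tables: "Change from baseline to the worst TEAE grade experienced by the subject during the study will be provided as shift tables". The list of parameters follows. Protocol 8.4.3 defines the shift tables in the same words.

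The same SAP section says where TEAEs come from: "The verbatim terms used in the electronic case report form (eCRF) by investigators to identify TEAEs will be coded" in MedDRA.

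The protocol restricts which laboratory findings become adverse events. Section 7.2 states: "Laboratory abnormalities that are of clinical significance will be recorded in Adverse Event eCRF". Section 7.4.1 states: "Abnormal laboratory tests occurring during the study should only be recorded in the AE section of the e-CRF if the disorder" has clinically significant symptoms, leads to discontinuation or significant added treatment, meets an SAE outcome, or is judged clinically relevant by the investigator. It continues: "Otherwise laboratory results should be reported in the corresponding section of the e-CRF". Section 7.2 also has laboratory abnormalities graded by CTCAE v5.0 in their own right.

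**The concern.** A shift table normally uses one graded variable on both axes. Here the starting point is a laboratory grade, and the end point, read literally, is an AE grade that exists only if an investigator recorded an event. A patient whose laboratory grade worsens without an AE entry would have no end point, or would appear unchanged. The SAP text gives no rule linking AE terms to laboratory parameters, so the literal table is also under-specified.

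This matters because Protocol 4.1 admits patients who are already abnormal: neutrophils down to 500/mm³, platelets down to 50 000/mm³, and ALT up to 3 x ULN (5 x ULN with liver involvement). A worst-grade table alone mixes abnormality present at entry with abnormality that arose on study. The shift table is the planned output that separates them.

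**Working it through.** The plan gives no figure to reproduce. The check compares the texts, counts the parameters exposed, and takes an illustration from data the protocol reports.

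**1. What the wording does.** The baseline side is a laboratory grade. The end point, a TEAE grade, comes from AE-form terms (SAP 11.7), and Protocol 7.4.1 keeps laboratory changes that meet none of its criteria off that form. The literal table therefore omits those changes.

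**2. Is it a slip?** Three features suggest so:
- The sentence closes a laboratory paragraph, just after the worst-grade table.
- The endpoint in SAP 8.3 and SAP 11.8 Table 3 is change from baseline in laboratory parameters, shown by CTCAE grade.
- The sponsor's earlier oncology analysis used the usual form: "Shift tables for the change from baseline to the worst grade on study for lymphocyte count and neutrophil count" (Protocol 1.2.1.3.2).

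**3. Parameters exposed.** From the list in SAP 11.7:
- Haematology 7 (haematocrit, red cells, white cells, neutrophils, lymphocytes, platelets, haemoglobin).
- Biochemistry 20 (direct bilirubin counted with total), including "gamma glutamyl transferase (GGT), creatinine, calculated creatine clearance".
- Coagulation 1 (D-dimer).
- Total 7 + 20 + 1 = 28.

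SAP 11.7.1 requires an AESI report for AST or ALT above 3 x ULN (above 5 x ULN with liver involvement and baseline ALT of 3 to 5 x ULN). It also names CPK increase as an AESI, without a threshold. That leaves 28 − 2 − 1 = 25 with no parameter-specific trigger. AST and ALT rises below the threshold are exposed too. Not all 28 parameters necessarily have CTCAE grades, and the documents do not say which do.

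**4. Illustration.** Protocol 1.2.1.3.1 and 1.2.1.3.2 give, for the earlier COVID-19 study, both AE rates and rates of new or worsening laboratory abnormality. Counts are back-calculated from the printed percentages. The AE denominator is 45. The laboratory denominator of 44 is inferred: all four laboratory percentages fit 44 and none fits 45.

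| Parameter | Reported as AE | Laboratory, new or worsening | Patients with laboratory change and no matching AE, at least |
|---|---|---|---|
| ALT | 5/45 = 11.1% | 29/44 = 65.9% | 29 − 5 = 24 |
| AST | 3/45 = 6.7% | 13/44 = 29.5% | 13 − 3 = 10 |
| GGT | 6/45 = 13.3% | 17/44 = 38.6% | 17 − 6 = 11 |
| Lymphopenia | 3/45 = 6.7% | 14/44 = 31.8% | 14 − 3 = 11 |

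The last column is a lower bound: it assumes every patient with the AE also had the laboratory change. The AE rate is between 11.1/65.9 = 17% and 13.3/38.6 = 34% of the laboratory rate. In the pooled oncology data (Protocol 1.2.1.3.2) no lymphopenia was reported among 419 patients, while 61/394 = 15.5% had a new or worsening lymphocyte decrease.

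**The case against.** The strongest reply is that no one would build the literal table. The sentence sits among laboratory outputs. SAP 11.7 defines treatment-emergent broadly, and Protocol 7.2 and 7.3.1 allow a laboratory finding to be an AE, so the phrase could mean the worst treatment-emergent laboratory grade. Past practice used laboratory data, and the table shells, which are not among the documents, may already be right. This supports calling it a slip. It does not rescue the wording: SAP 11.7 ties TEAEs to investigators' terms, Protocol 7.4.1 keeps other results off the AE form, and a programmer following the text would go to the AE dataset.

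Second, SAP Table 3 already gives laboratory change from baseline as CTCAE grade frequencies, and SAP 11.0 and 11.7 provide figures and listings. SAP 8.3 also keeps change from baseline in absolute lymphocyte count and neutrophil-to-lymphocyte ratio, although Table 3 carries only the ratio. This stands as a limit on the harm: graded values are not lost from the report. None of these outputs is specified as the baseline-to-worst cross-tabulation.

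Third, the count of 25 could be overread, because the general criteria of Protocol 7.4.1 apply to every parameter. That is correct. What the 25 lack is a numeric threshold or a naming as an AESI.

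Fourth, the earlier percentages do not predict this trial, since that study's AE-recording rules and time windows are not given. That is also correct; they show only that the two sources can differ widely.

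**Conclusion.** The concern holds, at minor severity. The sentence names the wrong data source for the shift-table end point and, if followed, omits new or worsening laboratory grades that were not recorded as AEs. Confidence in the wording error is high. How many patients would be affected here cannot be derived from the documents. The conclusion rests on reading TEAE as SAP 11.7 uses it and on sites following Protocol 7.4.1. Only the explicit baseline-to-worst cross-tabulation is at risk. SAP 6.0 makes the abbreviated report descriptive, and no decision rule depends on this table.

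**What to change.** In SAP 11.7, or in the table shells, replace the worst TEAE grade with *worst post-baseline NCI-CTCAE v5.0 laboratory grade, per parameter, from scheduled and unscheduled values*, using the baseline already defined in SAP 11.2. Keep laboratory-related TEAEs in the AE tables. Align Protocol 8.4.3 only if the protocol is amended for another reason. The cost is one phrase: laboratory values are already collected and graded, so no new data are needed. If the shells are already correct, only the SAP wording needs aligning.
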